Inclusion Criteria	Exclusion Criteria
Confirmed COVID-19 +	Stage 3 AKI by KDIGO criteria
Admission to ICU or step-down units at WVU	CKD stage 4-5
Foley catheter* and central line (or PICC) in place	Contraindications to Na bicarbonate therapy (e.g. met. alkalosis, severe heart failure)
Age ≥ 18 y	Urine pH > 7.0
	ECMO Patients

*Foley Catheter can be removed 72 hours after enrollment if appropriate documentation of urine output can be maintained

Urine alkalinization may also increase the elimination of certain drugs including hydroxychloroquine. We do not intend to exclude patients taking these drugs but it will be discussed in the consent form and with the treating physicians.

Intervention: The intervention is a modification/simplification of a standard protocol used for decades for the treatment of various drug toxicities (e.g. salicylate) or to mitigate kidney damage from chemotherapy.[25] Simplifications are intended to tailor the intervention to the management of COVID-19 patients and reduce or eliminate any additional staff exposure. We will continue urine alkalinization for 10 days or until patient is discharged from ICU or step-down unit or until the stage 3 AKI or a safety endpoint is reached. Urine pH will be measured at POC by dipstick. The major elements of the interventional protocol are shown in Table 2. Note, much of the monitoring (e.g. blood gases, calcium) is already performed for routine care. The protocol simply ensures that these measurements are timed to maximize patient safety and minimize burden on bedside nurses. The protocol has been developed with input from [name], Professor and Vice Chair for Research in the Department of Critical Care Medicine at the University of Pittsburgh.

Table 2. Protocol highlights
Sodium bicarbonate 225 mmol (225 mL of an 8.4% solution) intravenously over 1h
Recheck urine pH (dipstick) in 2-4 hours (from start of infusion)
Repeat boluses of intravenous sodium bicarbonate to achieve urine pH ≥ 7.2
Monitor urine pH every 2-4 hours until target is reached and then q6-8 hours
Sodium bicarbonate 8.4% solution should not exceed 900 ml (4 boluses) in 24h
Monitor plasma sodium, potassium, calcium every 12 hours and Acid-base status at least every 24 hours (Note: Arterial pH should not be > 7.50 , or venous > 7.55)
Acetazolamide (Diamox) can be administered at physicians' discretion to control systemic alkalinization and to help avoid fluid accumulation.

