Avoid fluid accumulation. If urine output does not increase to compensate for the increased fluid (it will in most cases, especially if kidney is protected), Lasix or Diamox can be added.
*If fluid balance cannot be maintained within +1L in 24 hours – protocol will be halted and resumed only if either the fluid balance can be correct to within +500mL in 24 hours or if the primary team decides that the patient has clinically appropriate fluid balance.

Data

collection: Information will be collected about patient demographics – date of birth, age, sex, race, weight, height, co-morbidities including but not limited to diabetes, hypertension, heart failure, coronary artery disease, previous cardiac surgeries, chronic kidney disease, cancers. Given the long history and familiarity with urine alkalinization, potential adverse effects (e.g. metabolic alkalosis, hypocalcemia) are well known. Data about renal function (creatinine, urine output, daily ins and outs), basic metabolic panel, blood gas, home medications, medications given during hospital stay and chart review to identify any relevant complications will also be performed. The provider survey will be performed using an online survey instrument and a link will be emailed to the provider to complete.

Sample collection: We will collect urine samples (1 before, 1 at 24 hours and 1 at 48 hours) from initiation of the protocol. Urine samples will be collected, processed and stored in accordance

with EH&S requirements for COVID-19 samples. At a later date and using alternative funding, we plan to analyze these samples for additional biomarkers either at WVU or at partner institution(s) in that study.[26] These biomarkers measure the cellular stress in the kidney[27] and will be examined in an ancillary study. The samples will be stored initially at the laboratories in WVU and then shipped to partner institution(s) for further testing of urine biomarkers as detailed above.

Statistical analysis: Descriptive statistics will be used for reporting: continuous variables expressed as median and interquartile range while categorical variables as frequency and percentages. No imputation will be performed and missing data will be treated as missing.

Aim 1: To determine feasibility and safety of a pragmatic urine alkalinization protocol for the prevention of AKI

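### The numeric fluid halt caps gain per day, while the trial's own overload event is a total; a cumulative trigger would close the gap cheaply

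*Combined protocol and SAP*

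**What the plan says.** The fluid rows of Table 2 (section 5, Approach) give one numeric halt: "If fluid balance cannot be maintained within +1L in 24 hours", the protocol is halted. It may be "resumed only if either the fluid balance can be correct to within +500mL in 24 hours". A second route back to dosing, with no figure or time window attached, applies "if the primary team decides that the patient has clinically appropriate fluid balance". The row before it is a standing instruction that opens "Avoid fluid accumulation. If urine output does not increase to compensate for the increased fluid" and then allows Lasix or Diamox. Another row leaves acetazolamide to the physician's discretion. Electrolytes are covered by "Monitor plasma sodium, potassium, calcium every 12 hours".

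On duration, the Intervention paragraph says "We will continue urine alkalinization for 10 days", ending earlier on discharge from the ICU or step-down unit, "or until the stage 3 AKI or a safety endpoint is reached". Safety endpoint is not defined.

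The Statistical analysis for Aim 1 lists volume overload among the monitored adverse events. It counts either a weight rise of more than 10% over admission during the protocol period, or ventilation or intubation because of overload.

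**The concern.** The halt and the harm are measured on different scales. The halt looks at one 24-hour window; the weight event adds up over as many as 10 days. A patient can stay inside the daily limit throughout and still accumulate enough to meet the event. In the published text, nothing with a number attached pauses boluses on the way there.

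This matters because the intervention is itself a sodium and fluid load, and the Significance section describes most patients as presenting with severe hypoxemia. Slow overload would count against the Aim 1 safety result and could also affect ventilator-free days, a secondary endpoint under Aim 2. The DSMB reviews adverse events after they occur, at set recruitment points, so it is not a bedside stop.

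**Working it through.** **Inputs.** From the documents: halt above +1 L per 24 h (Table 2); up to 10 days of treatment (Intervention); event at more than 10% of admission weight (Aim 1); bolus 225 mL, cap 900 mL per 24 h (Table 2). Assumed: 1 L retained = 1 kg; ten full days; diuretics unused or ineffective; no stage 3 AKI; no weight gained between admission and the first bolus.

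**Plan's own figure.** 4 boluses × 225 mL = 900 mL, which matches the stated cap.

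**Step 1: day of the event.** With steady net gain g (L/day) and weight W (kg), the event falls on the first whole day k ≤ 10 with k × g > 0.10 × W. At 70 kg and 0.99 L/day, 7 × 0.99 = 6.93 is below 7.0 and 8 × 0.99 = 7.92 is above it, so day 8.

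| Net gain from all fluids | 50 kg | 60 kg | 70 kg | 80 kg | 90 kg | 100 kg |
|---|---|---|---|---|---|---|
| 0.99 L/day | 6 | 7 | 8 | 9 | 10 | never |
| 0.7 L/day | 8 | 9 | never | never | never | never |
| 0.5 L/day | never | never | never | never | never | never |

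None of these rows trips the +1 L halt. At 0.7 L/day a 70 kg patient reaches exactly 7.0 kg on day 10, which does not exceed 10%.

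**Step 2: uncharted losses.** The halt uses charted balance, but the event uses weight. Suppose 0.3 L/day of loss goes uncharted (an assumption). A charted gain of 0.90 to 0.99 L/day is then a true gain of 0.60 to 0.69 L/day, and only patients of about 50 to 60 kg reach the event, on days 8 to 10. With 0.5 L/day uncharted, the true ten-day total is at most (0.99 − 0.5) × 10 = 4.9 kg, so no one at 50 kg or more does.

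**Step 3: would the sodium checks catch it?** Take starting sodium 140, body water a fraction t of weight (0.5 to 0.6), and retained fluid with sodium c (all assumed). At a 10% gain, Na = (140t + 0.1c)/(t + 0.1).
- c = 154: (84 + 15.4)/0.7 = 142.0 at t = 0.6; (70 + 15.4)/0.6 = 142.3 at t = 0.5.
- Passing the listed hypernatremia limit of 155 needs c > (155 × 0.7 − 84)/0.1 = 245 at t = 0.6, or (155 × 0.6 − 70)/0.1 = 230 at t = 0.5.

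So near-isotonic gain does not show on the 12-hourly checks. Retained bicarbonate alone would: with 900 mmol in 0.9 L fully retained, (140B + 900)/(B + 0.9) > 155 for body water B < 760.5/15 = 50.7 L, which is day 1 for anyone under 84.5 kg at t = 0.6.

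**Step 4: the resume test.** The +500 mL wording can mean the latest 24-hour balance, or the accumulated excess brought back to +500 mL. On the first reading, alternating +1.1 L (halt) and +0.5 L (resume) totals 5 × 1.6 = 8.0 L and passes 10% on days 7, 8 and 9 at 50, 60 and 70 kg. On the second reading this case does not arise.

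**Step 5: lead time of a 5% flag.** Replacing 0.10 by 0.05 in step 1 at 0.99 L/day gives days 3, 4, 4, 5 and 5 at 50 to 90 kg, which is 3 to 5 days before the event.

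**The case against.** The top row of the table is a corner case. It needs near-threshold true gain on every day, failing diuretics and no stage 3 AKI, since reaching that stage ends treatment. The exclusions (stage 3 AKI, CKD stage 4-5, severe heart failure) plausibly remove many of the patients most likely to retain fluid. Several consecutive days near +1 L would already breach the instruction against accumulation, so the scenario needs staff to pass over a written order. The trial is open-label partly so that complications can be managed. Much of the gain may be ordinary care fluid, which pausing boluses would not prevent. Table 2 gives highlights only, and a fuller bedside protocol may hold a limit on total gain.

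All of this stands, and it sets the size of the point. It does not remove it, because none of these safeguards puts a limit on total gain.

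Three stronger readings are tempting, and the documents support none of them:
- **Patients should be expected to become overloaded.** The calculation is a bound, and the plan gives no data on actual balances.
- **The bicarbonate alone would cause it.** The sodium checks would show that route first.
- **Dosing would carry on past the 10% event.** That event may well be a safety endpoint; the text does not say. If it is, treatment stops, but only once the harm has occurred.

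**Conclusion.** The point holds as an inexpensive patient-safety improvement. The published plan limits daily gain numerically and leaves total gain to judgement, although its own overload event is a total. At the upper bound the event could come on days 6 to 10 at 50 to 90 kg without the numeric halt firing. The exposure falls quickly to patients below 70 kg at 0.7 L/day and to none at 50 kg or more at 0.5 L/day, and uncharted losses reduce it again. Fluid gained between admission and the first bolus would work the other way. The result rests on the assumptions listed in the working and on Table 2 being the full set of fluid rules. It does not show that the protocol is unsafe as it would be run by attentive staff.

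**What to change.** Keep the +1 L daily rule and the primary team's discretion, and add a cumulative trigger to Table 2:

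1. Sum the daily ins and outs from the first bolus. When the total passes a pre-set share of admission weight below 10% (for example 5%, half the trial's own event), weigh the patient that day.
2. Pause boluses if measured gain over admission weight exceeds that share. Resume when it is corrected, or when the primary team judges the fluid balance appropriate. Charted balance only prompts the weight; measured weight decides the pause, which deals with uncharted losses.
3. In the same edit, state that measured gain above 10% is a safety endpoint that stops treatment, and say which reading of the +500 mL resume test applies.

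The cost is protocol wording, one running sum from data already collected, and extra weights for flagged patients among the 20 planned for the intervention arm. The Intervention paragraph aims to "reduce or eliminate any additional staff exposure", so the weight can be taken at an existing urine pH check, due every 6 to 8 hours once on target. The downside is false flags: at 0.5 L/day, patients of 50 to 90 kg are flagged on days 6 to 10 and none reaches 10% by day 10. A few boluses may be delayed. A fixed weighing schedule for both arms is a separate question and is not part of this change.

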AKI, defined as a sudden decrease in function and damage to kidneys is common among critically ill patients. The creatinine based Kidney Disease Improving Global Outcomes (KDIGO) criteria define AKI as an increase in serum creatinine by 1.5 times the baseline creatinine of by $\geq 0.3\text{mg/dL}$ [2]. The incidence of AKI at 2.1 per 1000 population is similar to that of heart attacks [3]. It is seen in 10-15% of all hospitalized patients but has been described in over 50% of critically ill patients [4, 5]. It has been described to be present among 15-25% patients with COVID-19 [6, 7].

AKI is not only common but is associated with 3-4 times higher mortality [8, 9], development of chronic kidney disease [10], end stage renal disease [11] and increase in healthcare expenditure [12]. There are no definitive therapies for AKI and treatment primarily rests on prevention of progression of AKI and management of its complications such as hyperkalemia, acidosis and volume overload. Approximately 6-13% of critically ill patients develop severe AKI that requires life-saving dialysis therapy [5, 13] but dialysis itself is associated with high mortality [13] and life-threatening complications such as infections. Therefore there is a great interest in developing therapies and treatment approaches that can prevent AKI in critically ill patients.

2. Hypothesis

We hypothesize that alkalization of urine is safe and effective to prevent development of AKI in patients with COVID-19

3. Significance

Although COVID-19 primarily affects the lungs and may cause severe hypoxemia, other organs including the GI tract, heart and kidney are affected. Acute kidney injury secondary to COVID-19 (COV-AKI) is reported to occur in about 15-25% of patients hospitalized with COVID-19 infection. [6, 7] However, AKI was much more common in non-survivors ($>50\%$). The majority of AKI cases are mild to moderate with renal replacement requirement in about 25% of AKI cases. But with COVID-19 taking the form of a pandemic, this has translated into thousands of patients needing dialysis. There are already reports of hospitals running out of dialysis machines to provide life-saving therapy critical for COVID-19 patients with AKI. As such there is a critical need to identify therapies that can delay the development or progression of AKI in these patients. Although kidney failure appears to occur late in the course, patients may begin to

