Primary feasibility outcome will be the proportion of patients treated who achieve >50% of urine measurements pH \geq 7.2 over the duration of treatment. Following specific adverse events will be monitored – hypokalemia (K<3.0meq/L), hypocalcemia (Ca<7.6mg/dL when corrected for albumin), Hypernatremia (Na>155meq/L), Volume overload (gaining weight >10% from admission weight during the protocol time-period, need for positive pressure ventilation or intubation due to volume overload), arrhythmias due to hypokalemia or hypocalcemia. To assess safety and feasibility, summary statistics including frequency, mean, standard deviation, median and interquartile range will be provided as applicable. Baseline data will be summarized comparing treatment groups over time. Chi-square/t-test will be used to compare the difference between treatment groups. Mixed model /ANCOVA will be used for repeated measurements over time.

As per the requirements of COE, a Data Safety Monitoring Board (DSMB) has been established that includes [name] [name], [name], [name] and [name] [name]. The DSMB will meet to review any adverse events after 5 and 25 patients have been recruited. In addition, as per the requirements of COE, the DSMB will meet to review any adverse events after the first 5 patients randomized to the interventional drug (open label arm) have been recruited and completed the study.

Aim 2: To determine the efficacy of urine alkalinization for prevention of AKI

Primary efficacy outcome will be the number of days alive and free of stage 2-3 AKI (up to 28) in each group. Secondary endpoints will include the proportion of patients developing stage 2-3 AKI (or stage 3 if already at stage 2 at enrollment); ventilator-free days to 28 and hospital-free days to 60. For AKI-free, ventilator-free, and hospital-free days, zero truncated negative binomial models will be implemented.

Severe AKI will be considered as binary outcome. Multivariable logistic regression will be used to assess the overall odds associated with treatment adjusted by baseline covariates (age, demographics, baseline renal function). Random forest decision tree regression method will be implemented to assess patient variable importance towards the outcome. Hazard will be assessed using cox proportional hazard model.

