Sample size determination: The study will be powered to achieve a 50% increase in the number of days alive and free of stage 2-3 AKI to day 28. We hypothesis an increase from 10 +/- 5 days to 15 +/- 5 days. The sample size needed to achieve this difference is 16 patients per group. We plan to enroll 20 patients per group for a total sample size of 40 patients. [name], Professor of Critical Care Medicine at the University of Pittsburgh and a co-investigator on this application is working towards a similar trial at the University of Pittsburgh (see attached letter of

support). The results from both these studies will then be pooled and changes in AKI rates, and survival will be examined.

Relevance to the current COVID-19 pandemic

There are at least four reasons why this study will have an important impact. First, when severe AKI does occur, mortality is very high.[6, 7] Preventing early AKI may reduce severe AKI as the disease progresses. Second, AKI has considerable effects on the immune system reducing a variety of immune functions[28] and hence might contribute to reduced host response. Third, this is unlikely to be the last β-coronavirus outbreak and different strains may cause even more AKI. Finally, the results of this study would provide critical proof of concept data that could be used to design other therapies to reduce viral RBD affinity. For example, alveolar pH could also be manipulated. Showing feasibility with this safe and available strategy could be the first step toward other related efforts.

C. REFERENCES

2. **KDIGO Clinical Practice Guideline for Acute Kidney Injury** [<https://kdigo.org/wp-content/uploads/2016/10/KDIGO-2012-AKI-Guideline-English.pdf>]

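### The trial is sized on a 5-day difference in mean AKI-free days, but no planned output for that outcome estimates the difference; the planned median can also sit at the 28-day cap in both arms

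*Combined protocol and SAP*

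**What the plan says.** - **Outcome** (5. Approach, Aim 2): "Primary efficacy outcome will be the number of days alive and free of stage 2-3 AKI (up to 28) in each group". A survivor who never has stage 2-3 AKI scores 28, and nobody can score more.
- **General summary rule** (5. Approach, Statistical analysis): "continuous variables expressed as median and interquartile range".
- **Means and SDs** appear only under Aim 1, for safety and feasibility: "summary statistics including frequency, mean, standard deviation, median and interquartile range will be provided as applicable". The same paragraph mentions chi-square and t-tests between groups, next to the sentence on baseline data.
- **Model for the days outcomes** (Aim 2): "For AKI-free, ventilator-free, and hospital-free days, zero truncated negative binomial models will be implemented". No effect measure or confidence interval is named.
- **Design target** (Sample size determination): "We hypothesis an increase from 10 +/- 5 days to 15 +/- 5 days", followed by "The sample size needed to achieve this difference is 16 patients per group". Planned enrolment is 20 per group.
- **AKI rates**: 3. Significance says that AKI "is reported to occur in about 15-25% of patients hospitalized with COVID-19 infection". 1. Background also cites AKI in more than half of critically ill patients. Neither rate is limited to stage 2-3. ICU mortality is called high, but no figure is given.

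**The concern.** The sample size commits the trial to a quantity: 5 more days, on average, alive and free of stage 2-3 AKI. A reader of the results will want the estimate of that quantity and its uncertainty. The plan supplies neither.

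- The median and IQR describe each arm. They do not estimate a mean difference, and with a hard cap the median can stop responding to treatment.
- A negative binomial model with its usual log link gives a ratio. The plan does not state the link, so this is an assumption. The zero-truncated form also assigns no probability to zero days. Yet zero is possible: Table 1 excludes only stage 3 AKI, and the secondary endpoint provides for patients already at stage 2 on enrolment, who may never clear it.

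At stake is whether the primary result can be set against the 10-to-15-day target. The same applies to ventilator-free and hospital-free days, which have the same form and the same model.

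**Working it through.** **1. The plan's own sample size is a comparison of means.** Inputs from Sample size determination: difference 5, with +/- 5 read as the SD. Assumed, because not stated: two-sided alpha 0.05, power 80%, no dropout.

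n per group = 2 × (1.960 + 0.842)² × (5/5)² = 15.7, rounded up to **16**. This matches the plan. By the normal approximation, power is about 81% at 16 per group and 89% at 20.

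**2. When the median sits at the cap.** Let p be the share of an arm that loses at least one day through death or stage 2-3 AKI. If p is below one half, the population median is 28. In a sample of 20 the median averages the 10th and 11th ordered values, so it equals 28 only if at least 11 patients score 28:

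P(arm median = 28) = P(Binomial(20, 1 − p) ≥ 11).

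The two arms are independent, so their probabilities multiply. This does not depend on when events occur or how long they last. The event rates below are assumptions, with treatment halving the control rate.

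| Control p | Treated p | P(control median 28) | P(both medians 28) |
|---|---|---|---|
| 25% | 12.5% | 0.986 | 98.6% |
| 30% | 15% | 0.952 | 95.2% |
| 40% | 20% | 0.755 | 75.3% |
| 50% | 25% | 0.412 | 40.6% |
| 60% | 30% | 0.128 | 12.1% |

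A simulation of 20,000 trials agrees with each figure to within half a percentage point.

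**3. The mean difference behind those medians.** This step needs an assumption on timing. Suppose an affected patient's score is uniform on 0 to 27, with mean 13.5. Each event then costs 28 − 13.5 = 14.5 days, and the true gain is 14.5 × (control p − treated p):

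- 25% vs 12.5%: 14.5 × 0.125 = 1.8 days
- 40% vs 20%: 14.5 × 0.20 = 2.9 days
- 50% vs 25%: 14.5 × 0.25 = 3.6 days
- 60% vs 30%: 14.5 × 0.30 = 4.4 days

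If every affected patient scored 0 instead, the gain at 25% vs 12.5% would be 28 × 0.125 = 3.5 days, with the same chance of 28 vs 28.

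**4. What the IQR adds.** In the same simulation, both medians are 28 and the lower quartiles are also equal in about 38% of trials at 25% vs 12.5%, 20% at 30% vs 15%, 4% at 40% vs 20%, and 0.4% at 50% vs 25%. The treated lower quartile is the higher one in 57%, 73%, 87% and 91% respectively.

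**5. How far the cited rates carry.** Suppose all cited AKI were stage 2-3. With AKI at 25%, p passes one half only if more than (0.50 − 0.25)/0.75 = 33% of patients without AKI die. With AKI at 15%, the threshold is (0.50 − 0.15)/0.85 = 41%. If instead more than half of patients had stage 2-3 AKI, the control median would fall below 28 without any further deaths.

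**6. Under the design assumption itself.** With mean 10 and SD 5, Cantelli's inequality limits the share at 28 to 25/(25 + 18²) = 7.2%. With mean 15 and SD 5 the limit is 25/(25 + 13²) = 12.9%. The medians would then be roughly 10 and 15 if the distributions are near symmetric, and well below 28 in any case. But a mean of 10 needs at least 1 − 10/28 = 64% of controls to lose days, which an AKI rate of 15-25% cannot produce without many other deaths.

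**The case against.** A reader might infer that a real effect would show as zero in this trial. The documents do not support that, for these reasons:

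- **The median rule is descriptive.** The between-arm analysis is the count model, which uses each patient's value rather than a median. This stands. At most one number per arm in a table is uninformative.
- **The rule is median and IQR.** Step 4 shows that the lower quartile separates the arms in most simulated trials. This stands too, though quartiles still do not estimate a mean difference.
- **The event rate is not known.** The 15-25% is for hospitalised COVID-19 patients, whereas the trial enrols ICU and step-down patients. The documents also cite more than 50% in the critically ill, and deaths add events. Against that, the 50% figure is any-stage and not specific to COVID-19, and 3. Significance describes most COVID-19 AKI as mild to moderate. The rate could lie on either side of one half.
- **Other outputs show event reduction.** The proportion developing stage 2-3 AKI, the logistic regression and the Cox model are all planned. True, but none is on the scale of days.
- **The t-test under Aim 1 would yield a mean difference.** It would if applied to the days outcomes. But it sits in the safety and feasibility paragraph, and Aim 2 assigns those outcomes to the count model.

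A reader might also infer that pooling with the second centre fails without means and SDs. The documents plan to pool for AKI rates and survival, do not name days, and do not say that only summaries will be exchanged.

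**Conclusion.** The point holds in a limited form and is minor. The trial is sized on a 5-day difference in mean days, and no output planned for the primary outcome estimates that difference or gives an interval for it. This rests on the text alone.

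The 28 vs 28 result is conditional. It is very likely (about 99% of trials at 25% vs 12.5%) if event rates are near the cited 15-25% and few other patients die. It falls to about 75% at 40% vs 20%, 41% at 50% vs 25%, and 12% at 60% vs 30%. It does not arise under the plan's 10 +/- 5 and 15 +/- 5. The halving of events is an assumption, and so is the timing behind the gains in days. The documents do not support the wider claim that the planned analysis would miss a real effect.

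**What to change.** In the Statistical analysis section, for AKI-free, ventilator-free and hospital-free days, add:

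1. the mean per arm;
2. the between-arm difference in mean days with a bootstrap 95% CI, over all randomised patients with the outcome, including those with zero days;
3. the percentage of each arm at the cap (28 or 60 days, as applies).

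Keep the median and IQR beside these.

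The cost is a few lines of wording and a little extra analysis, with no new data and no change to the sample size. The mean difference must be read alongside the distribution, because the outcome is skewed and capped; the percentage at the cap helps with that.

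### The named Aim 1 adverse events include no alkalosis or blood-pH event, although the plan itself foresees metabolic alkalosis and states blood pH limits

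*Combined protocol and SAP*

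**What the plan says.** All references are to section B.5 (Approach) of the combined protocol and SAP.

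- **Statistical analysis, Aim 1.** The list opens with "Following specific adverse events will be monitored". It names hypokalemia, hypocalcemia and hypernatremia, each with a laboratory cut-off. It then names volume overload, defined by weight gain or a need for ventilatory support, and arrhythmias attributed to low potassium or low calcium.
- **Data collection.** The plan says that "potential adverse effects (e.g. metabolic alkalosis, hypocalcemia) are well known". Blood gases and the basic metabolic panel are on the data list, and charts will be reviewed for relevant complications.
- **Table 1.** One exclusion reads "Contraindications to Na bicarbonate therapy (e.g. met. alkalosis, severe heart failure".
- **Table 2.** The intervention protocol asks for "Acid-base status at least every 24 hours" and notes that "Arterial pH should not be > 7.50 , or venous > 7.55". It allows acetazolamide "to control systemic alkalinization and to help avoid fluid accumulation".
- **Summary rules, Aim 1.** Safety and feasibility are to be described with general summary statistics where applicable. Groups are compared by chi-square or t-test, and repeated measurements by mixed model or ANCOVA. No individual adverse event has an analysis sentence of its own.
- **DSMB.** The board reviews any adverse events at stated recruitment points.

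**The concern.** The intervention is repeated intravenous sodium bicarbonate, so a systemic shift towards alkalosis is its most direct foreseeable harm, and the plan treats it as such in several places. Aim 1 is partly a safety aim, and its text goes to the trouble of naming specific events, most with numeric definitions. Alkalosis is not among them.

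What is at stake is the completeness of the safety statement. If the event table follows the list, it will show potassium, calcium, sodium, volume and certain arrhythmias by arm, and nothing on acid-base status. If someone adds an alkalosis row later, the case definition, the qualifying samples and the time window will be chosen in an open-label trial, possibly after results by arm are known. A statement that the protocol is safe would then be hard to defend on the one harm a reader would look for first.

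**Working it through.** No plan figure bears on this point, and no calculation settles it. The check is to set the adverse effects the plan foresees beside the events it defines.

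| Event named in the Aim 1 list | Definition given | Alkalosis, blood pH or bicarbonate? |
|---|---|---|
| Hypokalemia | K < 3.0 meq/L | No |
| Hypocalcemia | Ca < 7.6 mg/dL, albumin-corrected | No |
| Hypernatremia | Na > 155 meq/L | No |
| Volume overload | Weight gain > 10%, or ventilatory support needed because of overload | No |
| Arrhythmia | Only if caused by low potassium or low calcium | No |

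Count: 0 of 5.

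1. The Data collection text gives two examples of known effects, metabolic alkalosis and hypocalcemia. Hypocalcemia reached the Aim 1 list with a numeric cut-off. Metabolic alkalosis did not reach it at all.
2. Alkalosis cannot enter through another item. The three laboratory items are electrolytes, volume overload is a fluid measure, and the arrhythmia item is limited to potassium and calcium causes.
3. Table 2 contains numeric blood pH limits (arterial 7.50, venous 7.55), but as a monitoring note within the intervention protocol. The Aim 1 text does not carry them over as an event definition.
4. The general analysis sentences name no variable. A mixed model or ANCOVA could be fitted to blood pH, but a mean difference does not say how many patients had an excursion.
5. Chart review and DSMB review can bring cases to light. Neither says what counts as a case.
6. The acid-base schedule sits in the intervention protocol, and no schedule is stated for the control arm. Any by-arm count therefore also depends on how often each arm is tested.

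The data needed for an alkalosis result are thus largely on the collection list. What is missing is the event's place on the list and its definition.

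**The case against.** The strongest case on the other side has four parts.

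- **Capture is largely covered.** Treated patients have acid-base checks at least daily, blood gases are collected, charts are reviewed and the DSMB sees any adverse event. The list is also not said to be exhaustive. This stands. A reader might infer that alkalosis will go unmonitored or be left out of the report; the documents do not support that.
- **No listed event has its own by-arm reporting commitment.** All five rely on the same general summary and between-group sentences, and these could be applied to blood gas data too. This also stands. A reader might infer that alkalosis is singled out for weaker analysis; it is not. What is particular to alkalosis is its absence from the list and the lack of a case definition.
- **A count of patients with at least one high pH has its own weakness.** It rises with testing frequency, which may be greater in the treated arm, and it includes respiratory alkalosis. This stands as a reason to label the row descriptive and to show testing and pCO2 beside it. It is not a reason to have no row.
- **Only one secondary safety row is affected.** This stands as a limit on importance: the primary feasibility outcome, the efficacy outcome and the sample size are untouched.

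A reader might also link this to the stopping rule. Treatment continues "until the stage 3 AKI or a safety endpoint is reached", the term is not defined, and the plan does not say whether exceeding a pH limit qualifies. For fluid balance, by contrast, Table 2 says "protocol will be halted and resumed only if either the fluid balance can be correct to within +500mL in 24 hours". That is a separate gap. It applies to every listed event, and the plan is silent on it rather than contradictory, so it does not strengthen the present point.

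**Conclusion.** The omission is confirmed: 0 of 5 named Aim 1 adverse events concern alkalosis, blood pH or bicarbonate, although the plan names metabolic alkalosis as a known effect and a contraindication and states blood pH limits. Followed as written, the list gives no defined alkalosis count to put beside the electrolyte events.

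The gap is in definition and listing, not in monitoring or data collection. It should be closed because safety is a stated aim, the harm follows directly from the treatment, and the change is small.

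The conclusion assumes that the Aim 1 list is what will shape the safety event table, and that no other document outside the reviewed text defines the event. Table 2 presents itself as highlights, so some operational detail may lie elsewhere.

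**What to change.** These changes are for reporting only; no clinical rule is proposed.

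1. Add systemic alkalosis/alkalemia to the Aim 1 list, with a definition that the investigators fix before looking at data by arm. The limits already in Table 2 are one available reference; the choice is theirs.
2. Tabulate it by arm over the same post-randomisation window, in the final report and the DSMB tables, under the same general summary rules as the other events.
3. Beside it, summarise blood pH, bicarbonate and pCO2 by arm, with the number of tests per patient-day.
4. If the row counts patients with at least one qualifying value, state that it is descriptive, because testing may be more frequent in the treated arm and a pH flag also picks up respiratory causes.
5. Separately, ask the investigators to reconcile what the undefined safety endpoint in the Intervention text covers.

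The cost is wording in the SAP, the case report form and the DSMB tables, since blood gas and metabolic panel data are already on the collection list. The downsides are that control-arm blood gases may be incomplete and that the rate will be imprecise with 20 patients per arm. Showing the test counts makes unequal testing visible but does not remove its effect.
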